#### 3. SPUTUM

When possible freshly expectorated sputum sample will be collected from all study participants into a sputum pot for:

- (i) Gram stain Sputum pots are routinely available in the MAU and acute medical wards. The blood sputum pot and investigation request form will be labelled with the patient's name, hospital number, and date of birth in the standard way, and with the participant's unique trial code corresponding to the sequentially numbered study pack. This sample may be additional to any sputum sampling done by the medical team caring for the patient, and will be processed in the same way. The Investigation Request Form will be labelled with 'HTA Respiratory Infection Study'. The sputum and request forms will transported to the Microbiology Department (Public Health Laboratory) using the routine transport arrangements. The specimen will be processed using standard operating procedures
- (ii) *Sputum culture* The specimen collected for Gram staining (see above) will be cultured using standard operating procedures following receipt by the Clinical Microbiology Department.

#### 4. URINE

A freshly voided urine sample will be collected from all study participants into standard containers for:

- GROUP 1 ONLY: Near patient testing for pneumococcal antigen using the Binax NOW test by the Study Nurse on the MAU/Ward.
- GROUP 2 ONLY: Prompt testing in the laboratory for pneumococcal antigen using the Binax NOW test on fresh 20 ml concentrated urine.
- GROUP 3 ONLY: Deferred testing for pneumococcal antigen using the Binax NOW test on stored 20ml concentrated urine.
- **GROUP 1 ONLY**: Patients randomised to Group 1 will have near patient tests for pneumococcal antigen done by the study nurse in an area of the MAU/ward where urinalysis is done routinely. A description of the test kit and obstructions for doing the test is provided in Appendix X. On completion of the test the Study Nurse will:
  - (a) Record the test result in the CRF;
  - (b) Inform the team (i.e., the responsible nurse and/or doctor) that is providing clinical care of the patient of the rapid near patient test result (i) verbally; and (ii) by insertion of an adhesive label in the notes. The clinical team should be told that a negative test does not exclude infection with with *S. pneumoniae*.
  - (c) Document in the CRF the time that the team was informed, and who was told.

#### • GROUPS 2 and 3:

A **20**ml urine sample will be labelled with the participant's details, including name, date of birth, hospital number, and date of collection, AND in addition with the participant's unique trial code corresponding to the sequentially numbered study pack. The Investigation Request Form will be

labelled with 'HTA Respiratory Infection Study'. The specimens will be transported to the laboratory using the UHL transport system.

#### 6.1.15 Initial isolation status

The study nurse will record in the CRF the isolation status of the patient (i.e., whether nursed in an 'open' environment, or in a single cubicle) on the MAU/medical ward when the diagnostic samples are collected. The time of specimen collection – and thus a temporal record of isolation status – will be noted in the CRF.

#### 6.1.16 Initial investigations/procedures ordered by the medical team

The study nurse will record in the CRF details of the initial diagnostic studies carried out by the medical and nursing team providing clinical care, including, for example, ward urinalysis, FBC, blood biochemistry, cardiac enzymes, D-dimers, cardiac enzymes, blood gases, radiography, blood cultures, sputum culture, etc.

#### 6.2 Follow-up (Days 2, 3, 4,5,6 7,8,9,10, and 28)

#### 6.2.1 Time when diagnostic results were made available (Days 2, 3, 4, 7, and 10)

The times when the relevant diagnostic test results (See below) were made available to the medical and nursing team providing clinical care will be recorded in the CRF by reference to the APEX Pathology Computerised records system, and/or records held by the Department of Microbiology and Molecular Diagnostic Laboratory. Thus the times that the following test results were available will be entered into the CRF, even if the patient is discharged or has died:

Group 1:	
Rapid tests:	Rapid near patient test for influenza A and B (Quidel QuickVue influenza A and B)
	Near patient pneumococcal antigen test (Binax NOW test)
Conventional tests:	Viral culture test results (influenza A and B, RSV)
	Sputum Gram stain result
	Sputum culture result
	Blood culture result
Group 2:	
Rapid tests:	Rapid molecular tests for influenza A and B and RSV A and B,
	Laboratory pneumococcal antigen test (Binax NOW test) using concentrated urine
Conventional tests:	Viral culture test results (influenza A and B, RSV)
	Sputum Gram stain result
	Sputum culture result
	Blood culture result
Group 3:	
Conventional tests:	Viral culture test results (influenza A and B, RSV)
	Sputum Gram stain result
	Sputum culture result
	Blood culture result

## 6.2.2 Monitoring antimicrobial and antiviral treatment (Days 2, 3, 4,5,6 7,8,9, 10, and 28), and other new drugs prescribed for this illness

- The relationship between the results of diagnostic tests and antimicrobial therapy is a key measure. The study nurse will record the name(s), the time when first administered, the dose, frequency of administration, and route of delivery of all newly prescribed antimicrobials/antivirals in the CRF. Subsequent changes in dose, frequency of administration, and route of delivery must be documented, even when the same antimicrobial is prescribed. The number of days that each formulation was prescribed will be documented in the CRF by reference to the Prescription Chart.
- 2. The nature of antibiotic, i.e., whether 'narrow/targeted' or 'extended'-spectrum, will be entered subsequently in the CRF.
- 3. Resource use is a key measure in this study, so the name(s), dose, frequency, and route of administration of newly prescribed drugs (including routinely prescribed medication at a higher dose, such as insulin) and intravenous fluids will be recorded in the CRF, by reference to the Prescription Chart.
- 4. The name(s), dose, frequency, and route of administration of any newly prescribed antimicrobial drugs that are given to the patient on discharge will be recorded in the CRF by reference to the Prescription Chart.
- 5. Details of any antibiotics prescribed for this condition by the GP following discharge will be captured by a Questionnaire (Appendix I, see Pages 60 and 65). Patients will receive a reminder telephone call on Day 28 to return the Questionnaire by post.

#### 6.2.3 Isolation status (Days 2, 3, 4,5,67)

The relationship between isolation status and the results of diagnostic results is a key measure. The isolation status of the patient at mid-day on each of **Days 2, 3, 4,5,6 and 7** will be recorded in the CRF. The reason for isolation will be documented, since patients may be isolated for reasons other than an acute respiratory infection – e.g., winter vomiting disease, MRSA, diarrhoeal illness.

#### 6.2.4 Diagnostic tests, procedures, and other resource implications (Days 2, 3, 4, 7, 10, and 28)

The following resources used by study participants will be recorded in the CRF:

- 1. **Diagnostic tests/procedures** The number and type of all investigations and procedures that were carried out by the medical team, up to a maximum of 28 days (up to midnight of day 28) following admission, will be recorded in the CRF. This information will be obtained following discharge from hospital or death, by reference to APEX and examination of the case-notes and X-rays.
- Additional treatment/support The participant may require additional treatment or support, for example from a medical or nurse specialist, physiotherapist, nutritionists, occupational therapy, etc. This will be identified by reference to the medical records on discharge and recorded in the CRF.
- 3. **Discharge medication** The name, dose, frequency, and duration of any newly prescribed discharge medication (i.e., additional to regular prescriptions) will be recorded in the CRF for discharges occurring within 28 days of admission, by reference to the discharge letter.

- 4. **Hospital follow-up** The nature of further investigations (e.g., Chest-X-ray) and hospital follow-up visits that occur within 28 days of admission will be recorded in the CRF. This information will be captured by a Questionnaire (Appendix I, see Pages 60 and 65).
- 5. General practitioner consultations (Day 28) The number of occasions that patients were seen by their GP or deputising doctor after discharge (up to 28 days following admission), and whether it occurred in the surgery, another medical centre, or in the patient's home will be recorded in the CRF. This information together with the nature of any treatment received will be captured by a Questionnaire (Appendix I, see Pages 60 and 65).

#### 6.2.5 Pyrexia (Days 2, 3, 4, 7, 10)

The study nurse will monitor the temperature chart and record when the patient first became apyrexial (temperature  $\leq 37.2^{\circ}$ C), and remained so for a period of at least 24 hours.

#### 6.2.6 Supplemental oxygen and CPAP (Days 2, 3, 4, 7, 10)

The study nurse will record in the CRF whether the study participant required supplemental oxygen (and CPAP) during days 1-10 of admission, and when supplemental oxygen (and CPAP) was no longer necessary (i.e., not required for a period of at least 24 hours).

#### 6.2.7 Admission to ICU and ventilatory support (Days 2, 3, 4, 7, 10)

The study nurse will document in the CRF whether the patient was admitted to an Intensive Care Unit (ICU) during the first **10 days** of admission and whether he/she required ventilatory support. The total duration of stay on the ICU will be documented in the CRF.

#### 6.2.8 Blood sampling for humoral and cell-mediated immunity to the pneumococcus.

Patients whose pneumococcal antigen test is positive (groups 1&2), and an equivalent number of people with a negative antigen test, will have a 25ml blood sample collected on one occasion during the first 5 days of hospital admission for tests of humoral and cell-mediated immunity to the pneumococcus.

#### 6.2.9 Quality of Life assessment (Days 7 and 28)

All patients will be assessed by the EuroQol (Appendix I) on Days 7 and 28, and the results recorded in the CRF. Patients who have been discharged will be assessed by post using a questionnaire, or by a simple telephone interview.

#### 6.2.10 Hospital discharge (Duration of hospitalisation/discharge diagnosis)

The duration of hospitalisation (until discharge or death) and discharge diagnosis will be obtained from the hospital activity analysis (i.e., computerised records) and recorded in the CRF.

#### 6.2.11 Deaths

Deaths that occur within a maximum **28 days** of hospitalisation will be recorded in the CRF. [Note: the principal investigator MUST be notified by the study nurse of all deaths that occur within 28 days of admission and of the patient's study group]. [Note; the letter informing the GP of their patient's participation in the study will ask the GP to inform the investigators by fax should the patient die following discharge within 28 days of hospitalisation].

#### 6.2.12 Convalescent serology (Day 10-90)

A 10ml convalescent blood sample will be collected from survivors at **10-90** days. The serum will be saved for paired acute and convalescent serology for influenza and RSV. The blood sample will be labelled with the participant's details, including name, date of birth, hospital number, and date of collection, AND in addition with the participant's unique trial code corresponding to the sequentially numbered study pack. The blood sample will be transported to the laboratory using the UHL transport system.

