the different microbiological tests for influenza, RSV, and *S. pneumoniae*, together with the results, will be documented

*Treatment* The nature (name, dose, frequency, and route of administration) of all antimicrobials given to all patients within 10 days of admission will be documented. Note will be made of when 'broad-spectrum' treatment is switched to 'narrow-spectrum treatment'; when intravenous antibiotics are switched to oral therapy; and when antibiotics are discontinued. The requirement for supplemental oxygen will also be documented.

*Isolation status, admission to ITU, and ventilatory support* A record will be kept of (i) the patient's isolation status during the first 7 days of admission, and whether the patient was admitted to an ITU and/or required ventilatory support (including ward-based CPAP) during the first 10 days of admission.

*Pyrexia* The time (24 hr clock and date) during the patient's first 10 days of hospitalisation (or until death, if relevant) when the patient first became apyrexial (temperature  $\leq 37.2^{\circ}$ C), and remained so for a period of >24 hours will be recorded.

*Convalescent serology* A convalescent blood sample will be collected for paired acute and convalescent serology for influenza and RSV at 10 -90days.

*Diagnostic studies* The nature and results of all diagnostic studies (e.g., chest radiograph, ECG, full blood count, cardiac enzymes, PaO2) carried out by the medical team will be recorded.

*EuroQol* The health status of all patients will be assessed by the EuroQol on days 7 and 28. Where patients have been discharged the EuroQol will be assessed by telephone interview of the patient or by postal questionnaire or by proxy (Appendix I).

*Humoral and cell-mediated immunity to the pneumococcus.* Patients whose antigen tests for the pneumococcus are positive and an equivalent number of people whose pneumococcal test is negative will be bled on one occasion only within 5 days of hospital admission, for tests of cellular and humoral immunity to the pneumococcus.

Physical Activity Questionnaire will be completed on day 2 or 3.

*Deaths* Deaths that occur within a maximum 28 days of hospitalisation will be identified by the study nurse and recorded in the CRF. [Note: the principal investigator MUST be notified by the study nurse of all deaths that occur within 28 days of admission and of the patient's study group].

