#### 7.3 Definitions of influenza, RSV and S. pneumoniae positivity

Influenza positive Patients will be considered influenza positive if:

- The Quidel QuickVue Influenza A and B test is positive, and/or
- The multiplex PCR is positive, and/or
- Viral culture is positive, and/or
- Serology results indicate influenza infection (e.g., 4-fold increase in influenza A H3N2, H1N1, or influenza B HI antibody from acute to convalescent sera).

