#### **RSV positive** Patients will be considered RSV positive if:

The multiplex PCR is positive, and/or

- Viral culture is positive, and/or
- Serology results indicate RSV infection (e.g., ≥4-fold increase in RSV antibodies from Day 1 to Day 30).

S. pneumoniae positive Patients will be considered influenza positive if:

- The Binax NOW S. pneumoniae antigen test is positive, and/or
- Blood culture is positive, and/or
- Sputum culture is positive, AND the sputum sample is macroscopically purulent, AND the sputum sample reveals increased numbers of polymorphonuclear leucocytes, AND the Gram stain is positive, AND there is moderate-to-high amounts of growth, according to criteria used by the laboratory.

Evaluations will be based on: (i) populations whose cardio-pulmonary illness is confirmed as due to influenza, RSV or *S. pneumoniae*, and (ii) the study groups comprising all people who are investigated by the different strategies under investigation (rapid near patient tests, *versus* rapid molecular diagnosis, *versus* conventional laboratory tests).

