  First, the proportion of patients with *S. pneumoniae* infection in Groups 1, 2, and 3.
  Second, to better define the burden of influenza and RSV, the proportion of all patients with (i) influenza, and (ii) RSV, who die.
- 3. Quality of life, as measured by EuroQol, and quality adjusted life years generated during the 28 days after admission, will be assessed:
  - (a) In all patients in Groups 1, and 2 in comparison to Group 3.

- (b) Second, in patients in patients with (i) influenza, (ii) RSV, and (iii) *S. pneumoniae* in Groups 1, and 2, in comparison to Group 3.
- 4. Use of isolation facilities
  - (a) The time from admission to the MAU to the time of admission to a single room (isolation cubicle) will be compared for patients with confirmed influenza or RSV in Groups 1, 2, and 3.
  - (b) The proportion of patients with influenza or RSV in Groups 1, 2, and 3 who are isolated at any stage during the first 120 hours of the admission.
  - (c) The proportion of patients with *S. pneumoniae* infection in Groups 1, 2, and 3 who are inappropriately isolated for >12 hours.

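### Serology-only influenza and RSV cases must survive to the convalescent bleed, so the pooled 28-day case-fatality proportion in endpoint 2(f) is biased downwards by a modest amount

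*Protocol*

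**What the plan says.** Four parts of the protocol bear on this.

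- **Who is bled.** Section 6.2.12: "A 10ml convalescent blood sample will be collected from survivors at" 10-90 days. Section 4.1 repeats the window: "A convalescent blood sample will be collected for paired acute and convalescent serology for influenza and RSV at 10 -90days".
- **Who is a case.** Section 7.3 joins its criteria with and/or, so each is sufficient alone. For influenza they are QuickVue, multiplex PCR, culture, or serology: "Serology results indicate influenza infection (e.g., 4-fold increase in influenza A H3N2, H1N1, or influenza B HI antibody from acute to convalescent sera". For RSV they are PCR, culture, or serology: "Serology results indicate RSV infection (e.g., ≥4-fold increase in RSV antibodies from Day 1 to Day 30".
- **What is reported.** Endpoint 2(f) in section 7.5.1 includes "the proportion of all patients with (i) influenza, and (ii) RSV, who die", and its stated purpose is to describe the burden of the two viruses. Endpoints 2(d) and 2(e) report intensive care and ventilatory support over the first 10 days in the same patients.
- **The death window.** Section 4.1: "Deaths that occur within a maximum 28 days of hospitalisation will be identified by the study nurse and recorded in the CRF".

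No section removes serology-only cases from these proportions.

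**The concern.** Case status depends partly on surviving the period over which the outcome is counted. Take two infected patients whose admission swabs are negative on every test. One dies on Day 6 and is never classified as a case. The other survives, is bled, shows a four-fold rise and joins the denominator. Serology therefore adds survivors to the denominator without the corresponding early deaths.

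For influenza, anyone bled after Day 28 has already outlived the whole death window. For RSV, a rise measured at Day 30 means that no serology-only case can be a 28-day death.

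These proportions are meant to describe how severe influenza and RSV are in this population. Section 1.11 makes an important effect on mortality one of the conditions that would justify rapid testing. Section 2.2 also hypothesises that the two viruses have similar characteristics and burden. A serology-only share that differed between them would distort that comparison.

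**Working it through.** **Denominators.** Section 7.1 expects 10% of 2752 elderly participants to have influenza and 5% to have RSV: 2752 × 0.10 = 275.2 and 2752 × 0.05 = 137.6. These reproduce the stated 275 and 138. The protocol states no expected case fatality for either virus.

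**Quantities**

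- c, true 28-day case fatality. Assumed 10%, with 2.5% and 20% as bounds. Section 1.5 gives about 2.5% for pneumococcal pneumonia, used only as a proxy. Section 1.4 gives up to 20% for RSV outbreaks in residential care.
- s, share of true cases detectable only by serology. Not given. Section 1.6 quotes 92% sensitivity for the multiplex PCR and says that culture plus serology has served as the reference for molecular diagnosis. That suggests about 8% of influenza cases missed by PCR, before culture or QuickVue recovers some. The figure is not from elderly inpatients, so it is indicative only. I use 8%, 10% and 20%.
- d, share of 28-day deaths that precede the bleed. Not given. I use 1 and 0.75.
- q, share of eligible survivors who are bled. I use 1 and 0.8; the latter borrows the 20% dropout allowance in section 7.4.

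**Formula.** With the same c in swab-detected and serology-only cases:

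reported = c[(1 − s) + sq(1 − d)] / [(1 − s) + sq(1 − cd)]

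With q = 1 this is c(1 − sd)/(1 − sdc).

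**Worked line**, c = 0.10, s = 0.08, d = 1, q = 1: 0.092/0.992 = 9.3%.

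| s | d = 1, q = 1 | d = 0.75, q = 1 | d = 1, q = 0.8 |
|---|---|---|---|
| 8% | 9.3% | 9.5% | 9.4% |
| 10% | 9.1% | 9.3% | 9.3% |
| 20% | 8.2% | 8.6% | 8.5% |

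In the first column the relative understatement is about 7%, 9% and 18%.

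**Other fatality values** (d = 1, q = 1). A true 2.5% is reported as 2.3%, 2.3% and 2.0% at the three shares. A true 20% is reported as 18.7%, 18.4% and 16.7%.

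**In counts.** With 275 influenza cases and 27.5 deaths, the deaths lost are 27.5 × s = 2.2, 2.75 and 5.5. At s = 8% the result is (27.5 − 2.2)/(275 − 2.2) = 25.3/272.8 = 9.3%, as above.

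**Intensive care.** Let i be the true proportion admitted and m the fatality among those admitted. With q = 1, reported = i(1 − sdm)/(1 − sdc). Assume i = 5%, c = 10%, s = 10%, d = 1:

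- m = 10% (equal to c): 5.0%, no bias.
- m = 30%: 0.05 × 0.97/0.99 = 4.9%.
- m = 30%, but 90% of intensive-care survivors bled against 60% of the others: 5.04%, so the direction reverses.

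**With serology-only cases left out** (s = 0), the formula returns c exactly.

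**The case against.** The strongest reply is that early deaths are not shut out of being cases. Section 6.1.14 provides for PCR on the admission swab in every patient, promptly in Group 2 and deferred in Groups 1 and 3, and culture is done for all. Only the serology route closes at death. This stands, and it is why the effect is modest.

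A reader might infer that RSV is hit hardest because culture is insensitive for it. The documents do not support that. Section 1.7 calls PCR a sensitive and specific method for RSV, and lists the complement fixation test, itself serological, among the insensitive ones. The RSV serological assay is not named. Brief shedding and low nasal titre could raise the RSV share, but no figure is given. Nothing in the documents supports serology-only shares of 30% or 40% either.

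A reader might also infer that the intensive-care and ventilation proportions are understated. That does not follow: the effect there is indirect and smaller, and it can vanish or reverse.

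The affected figures are pooled, descriptive and unpowered, and sampling error is larger than the bias. The 95% half-width around 10% is about 3.5 points with 275 cases and 5.0 points with 138. That limits the importance, but the bias is systematic and does not shrink as numbers grow.

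Finally, section 1.6 says that neither culture nor serology alone is sensitive enough, so counting serology is a reasoned choice. If serology-only cases are milder, fatality among swab-positive cases alone would overstate the burden. This is a good reason to report serology-only cases separately, but not to mix them into a proportion in which their early deaths cannot appear.

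**Conclusion.** The concern holds for the 28-day influenza and RSV case-fatality proportions in endpoint 2(f). As the protocol is written, serology-only cases add to the denominator and cannot add deaths before the bleed, so the proportion is biased downwards. For a true 10%, the reported value is about 9.3%, 9.1% or 8.2% at serology-only shares of 8%, 10% or 20%, if all deaths precede the bleed and all survivors are bled. It lies closer to 10% otherwise. The 8% share is indicative for influenza; the other shares, the timing of deaths and the 10% itself are assumptions.

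The downward direction rests on equal fatality in swab-detected and serology-only cases, or on complete bleeding of survivors. If serology-only cases were milder and many survivors were not bled, the two effects would partly offset.

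The point does not extend further. The group comparisons of death, intensive care and ventilation in section 7.5.1 concern *S. pneumoniae*, whose definition uses no serology. The mortality comparison between the three groups in section 7.6 is not stated to be restricted to confirmed cases. No bias has been shown in the other influenza and RSV subgroup analyses.

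**What to change.** In sections 7.3 and 7.5.1, state that for the pooled influenza and RSV burden proportions in 2(f), and in 2(d) and 2(e) so that the denominators agree, a case is defined by tests on admission specimens, which are available whether or not the patient survives. Report serology-only cases in a separate row, labelled as cases among survivors to the convalescent bleed.

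Keep serology in the reference for diagnostic accuracy, and leave the other influenza and RSV subgroup analyses unchanged.

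Reconcile the Day 1 to Day 30 comparison in the RSV definition with the Day 10-90 window in sections 4.1 and 6.2.12.

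The cost is about one sentence in each section and a somewhat smaller denominator for these proportions. No new data are needed.
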